Study Protocol

Official Title: Effectiveness of Contingency Management in the Treatment of Crack Addiction for Individuals Living in the “Crackland” Region. A Single-Blind Randomized Controlled Trial

Identifier: NCT03345394

Protocol ID: FAPESP 2017/05371-8

Primary Investigator: [name] [name].
[name]. E-mail address:
[contact] ([name])

Sponsor: Paulista Medical School of the Federal University of São Paulo

Sao Paulo, 5th of January 2018

Title:

Effectiveness of Contingency Management in the Treatment of Crack Addiction for Individuals Living in the “Crackland” Region. A Single-Blind Randomized Controlled Trial

Study personal and roles:

[name]	Principal Investigator	Responsible for all study related issues
[name] [name] [name] [name] [name] [name] [name] [name]	Co-Investigators	Study design, data management, analyses and interpretation of the findings
[name]	Project Manager	Data management, addresses IRB issues, conducts randomization
[name]	Study Coordinator	Data collection, screening, consent

Grant funding:

This study was funded by the Research and Innovation grant for Prevention of Mental Disorders and Abuse of Alcohol and Other Drugs (*Pesquisas e Inovações em Prevenção de Transtornos Mentais e Uso de Álcool e Outras Drogas*) from the Brazilian Ministry of Health (TED #176/2017). [name] received two postdoctoral fellowship grants from *Fundação de Amparo à Pesquisa do Estado de São Paulo* (FAPESP)- processes nº 2017-05371-8 and nº 2017-22004-9.

Background:

Crack cocaine use disorder (CUD) is a severe health problem in Brazil, with the country being reported as the biggest crack market in the world. Contingency Management (CM) is one of the most effective treatments for CM however its effectiveness has never been evaluated in Brazil.

Purpose:

The objective of this study was to evaluate the effectiveness of incorporating CM into a public treatment program in Brazil.

Study Design:

Single-Blind Randomized Controlled Trail where researchers will be blinded.

Study duration:

Study duration was from December 2017 to December 2020. Data collection occurred from January 2018 to March 2020.

Study Centers:

This study was conducted by a partnership between the Federal University of Sao Paulo and the Program of excellence in Addiction Research Program from Washington State University. All stages of the screening, intervention and data collection processes were conducted at *Unidade Recomeço Helvétia*, a public ambulatory treatment program for CUD located in downtown Sao Paulo, Brazil.

Objectives: Primary objective was to evaluate the effectiveness of incorporating CM into a public ambulatory treatment program for CUD in São Paulo, Brazil in promoting crack cocaine abstinence for treatment seeking individuals with CUD. The secondary objective of this study was to determine the feasibility and acceptability of incorporating CM into a public ambulatory treatment program for CUD in São Paulo, Brazil.

Power: Sample size calculations were conducted according to the following parameters: significance level ($\alpha = 0.05$), power ($1 - \beta = 0.8$), χ^2 test (contingency table under degrees of freedom = 1), and effect size ($w = 0.3$). These parameters resulted in a necessary sample size of at least 88 subjects.

Randomization:

Randomization was carried out using permuted blocks randomization with the inclusion of gender and baseline urinalysis result covariates for stratification to balance group-samples.

Inclusion Criteria:

The inclusion criteria was as follows: 1) being 18 years old or older; 2) having a current diagnosis of moderate to severe CUD according to *The Diagnostic and Statistical Manual of Mental Disorders, 5th Edition* (DSM-V); and 3) consenting to participate in the study. There were no exclusion criteria.

Recruitment:

Individuals with CUD seeking treatment at URH will be screened for eligibility.

Sample size: A total of 111 subjects were screened and 98 enrolled in the study. Of these 98 subjects, 48 subjects were randomized to the control condition and 50 subjects to the were randomized to the experimental condition.

Intervention:

After randomization participants will receive 12 weeks of treatment in either the control condition or the experimental condition.

Control condition:

Participants allocated to the control condition will receive the standard treatment provided by URH. The URH is an open-doors facility that provides a variety of interventions, ranging from harm reduction to abstinence-based interventions for crack users in different stages of recovery. URH offers access to showers, toilets, a beauty salon, and a gym. It also provides several group

activities, such as self-help group counseling as well as footcare, percussion, clown, and experimental kitchen classes.

Experimental condition:

Participants allocated to the control condition will receive the standard treatment provided by URH in association with CM. The CM intervention will consist in providing vouchers with monetary value contingent to the submission of a negative cocaine urinalysis (UA).

The value of the vouchers will start at \cong US\$2.00 (as of December 2020, one US dollar was approximately five Brazilian reais) for the first negative UA submitted. Vouchers will increase by \cong US\$1.00 for every consecutive negative cocaine UA submitted up to a maximum of \cong US\$5.00. In addition, a \cong US\$5.00 bonus will be given if both weekly UAs test negative for cocaine. Participants who failed to submit a negative UA will not receive any vouchers that day and the value of future vouchers will reset to \cong US\$2.00. If abstinent for the entire 12 weeks of treatment participants can earn up to \cong US\$185.00 in vouchers.

To reduce screening costs and reinforce acknowledgment of recent use, participants will be asked prior to submitting the UA if they have used cocaine in the last four days. Participants will be encouraged to submit the UA if they state that they have been abstinent but will not be required to submit a sample if they disclose recent crack cocaine use. Instead, they will be congratulated for admitting recent use (UA will be coded as positive by research staff) and will receive a token with \cong US\$0.50 value. This token may be added to a future voucher's value, contingent upon the submission of a future negative UA. This procedure, we term CM Banking, intends to reduce costs related to screening and increase attendance among participants struggling to achieve abstinence. Vouchers may be exchanged for any type of goods available in the surrounding community immediately after the submission of a negative UA (with the exception of alcohol and tobacco products). After deciding on a desired commodity, participants will inform their respective providers. The provider will then accompany the participant to make the purchase.

Data collection:

Data were collected at baseline and twice weekly during the 12 weeks of the intervention.

Assessments:

Assessments include a structured sociodemographic questionnaire and questions related to the pattern of substance use and previous treatment history.

The following assessments were also collected:

- Diagnostic and Statistical Manual- 5^o edition (DSM-V)
- Alcohol, Smoking and Substance Involvement Screening Test -ASSIST).
- Brief Symptom Inventory- BSI
- Barrat Impulsivity Scale- BIS)
- Risk Assessment Battery -RAB)
- Abon Biopharm cocaine urine test which is capable of detecting 300ng/ml or more of benzoylecgonine in the urine.

Primary outcome:

Our primary outcome was objective verification of crack cocaine abstinence assessed as negative cocaine UAs tested twice weekly for 12 weeks.

Secondary outcome:

Treatment retention as a secondary outcome. Retention was defined as the number of weeks elapsed between treatment intake and dropout.

Statistical analyses plan.

The primary endpoint of this study will be objectively verified abstinence based on the UA results collected twice weekly during the 12 weeks of intervention. Secondary endpoint will be duration of treatment retention.

Publication and data sharing policy:

The preparation and submittal for publication of manuscripts containing the study results shall be in accordance with a process determined by mutual written agreement among the study Sponsor and participating institutions. The publication or presentation

Conflicts of interest:

No conflicts of interest have been reported.

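### Does having research staff code disclosed-use urine tests as positive contradict the claim that researchers are blinded?

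*Combined protocol and SAP*

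**What the plan says.** The title reads "A Single-Blind Randomized Controlled Trial" and names no blinded group. Study Design is the only place that names one: "Single-Blind Randomized Controlled Trail where researchers will be blinded". The table of study roles lists a principal investigator, co-investigators (who include the analysts), a project manager (who randomizes and shares data management) and a study coordinator, whose entry is "Data collection, screening, consent". None is marked as blinded or unblinded, and no blinding procedure is described.

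The Experimental condition section sets out the voucher scheme and then a disclosure step: "participants will be asked prior to submitting the UA if they have used cocaine in the last four days". A participant "will not be required to submit a sample if they disclose recent crack cocaine use", and "UA will be coded as positive by research staff". The participant then gets a token worth about US$0.50, which can be added to a later voucher "contingent upon the submission of a future negative UA". The stated reason is practical: "This procedure, we term CM Banking, intends to reduce costs related to screening". The Control condition paragraph mentions no such question and does not exclude one.

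The Primary outcome and Statistical analyses plan sections define the endpoint as abstinence verified by UAs taken twice weekly for 12 weeks.

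**The concern.** A blinding statement tells readers that the people producing the data did not know the allocation. Here some primary-outcome records are made by research staff, from self-report, under a procedure that carries the intervention's name and hands out something only voucher recipients can use. Anyone applying that rule can probably tell that the participant is in the CM arm. If these staff are the researchers of the Study Design sentence, the sentence is untrue for them.

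Two things would be at stake. One is bias: an outcome recorder who knows the arm may record differently. The other is unequal ascertainment: if the rule applies in CM only, some CM results rest on self-report without a test and control results do not, although the endpoint is described as objectively verified.

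**Working it through.** The documents give no figure for blinding or for the number of disclosure-coded UAs, so most of the check is reasoning. The plan's only design figure, a minimum of 88 subjects, reproduces: (1.960 + 0.842)² / 0.3² = 87.2, rounded up to 88. It does not depend on blinding.

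**1. Is there a contradiction?**

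- Study Design speaks of researchers; the disclosure step speaks of research staff. Nothing says they are the same people.
- The roles table separates analysis (co-investigators) from data collection (study coordinator), so a blinded analyst and an unblinded collector can coexist.
- Participants know whether they receive vouchers, and providers accompany them on purchases. Neither group can be blinded, which leaves investigators or analysts as the natural meaning. On that meaning both the title and Study Design hold.
- The documents do not say that the person who enters the code also hands over the token. That the coder knows the arm is a strong inference, because the rule is part of the CM procedure, but it is not stated.

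**2. Could knowledge of the arm change a code?**

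For a disclosed-use visit the rule is: disclosure leads to a positive code. The coder makes no reading and uses no discretion, so the code is the same whether or not the coder knows the arm. The bias from unblinded coding of these records is therefore zero by construction.

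**3. Which way does the coding rule itself push, if it is CM-only?**

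- Compared with testing the same visit: a sample that would have been positive keeps its code; one that would have been negative becomes positive. The CM negative rate stays the same or falls.
- Compared with a missed visit: if missed visits count as positive, nothing changes. If they are left out, adding a positive record lowers the rate or leaves it unchanged.

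In each case the rule cannot favour CM.

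**4. What scale could it have?**

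- Scheduled UAs per participant: 2 × 12 = 24.
- CM arm: 50 × 24 = 1,200 scheduled UAs.
- Taking all 1,200 as the denominator (an assumption, since the plan states none), 12 disclosure-coded UAs that would have tested negative lower the CM rate by 12 / 1,200 = 1.0 percentage point.

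This is a unit conversion, not an estimate. It would be the same with fully blinded coders, so it says nothing about the blinding claim.

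**5. Are such records likely?**

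A negative UA earns about US$2.00 to US$5.00, keeps the escalation going and may bring a further US$5.00 weekly bonus. Disclosure earns about US$0.50, usable only after a later negative UA. The smallest voucher is 2.00 / 0.50 = 4 times the token. A participant who expects a negative result has little reason to disclose.

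**The case for a change.** The strongest case for acting is that a reader meets single-blind in the title and blinded researchers in Study Design, and cannot tie the claim to anyone. The people who code some primary-outcome records are called research staff by the document itself, so the ordinary reader will take them to be covered. Naming the blinded role, saying whether the disclosure rule also ran in control, and counting tested and disclosure-coded UAs by arm would cost a sentence or two and a small table, and could still be done after data collection ended in March 2020. Some disclosed-use visits might also have tested negative: a four-day recall question asked on average every 7 / 2 = 3.5 days can catch the same use twice.

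Part of this stands. The word researchers is undefined. The staff who apply the disclosure rule should not be assumed blinded. The documents do not say who reads the tested samples, or whether control participants were asked the same question.

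The step from there to a fault in the plan does not stand. The title names no group and remains true if any one group was blinded. The handling of disclosed-use UAs is not missing, since the document fixes it as positive. The extra reporting would describe how results arose without altering any of them.

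**Conclusion.** No change to the plan follows. The blinding sentence is under-specified, but it is not shown to be false: it holds if investigators or analysts were the blinded group, and the documents allow that reading. The feature that seems to break the blind is a mechanical rule under which knowing the arm cannot alter the code, so no bias from unblinded coding is shown. Any effect of the rule itself lowers the CM negative rate or leaves it unchanged, which is conservative for a claim that CM works. Its size cannot be computed without the number of disclosure-coded UAs and the share that would have tested negative.

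This rests on three assumptions: that the rule was applied as written, that it was confined to the CM arm (a strong inference from its place, its name and the token), and that tested samples were read against the assay's stated threshold in both arms. If the rule also ran in control, the difference in ascertainment largely disappears. What remains is a gap in description, of the kind authors ordinarily fill when they report who was blinded.

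### Randomization is stratified by gender and baseline urinalysis, but no planned analysis carries those factors; an unadjusted analysis would lose some power and precision if baseline urinalysis is prognostic

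*Combined protocol and SAP*

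**What the plan says.** - **Randomization** describes permuted blocks "with the inclusion of gender and baseline urinalysis result covariates for stratification to balance group-samples". Block size is not given.
- **Power** sizes the trial on a chi-square "test (contingency table under degrees of freedom = 1), and effect size" w = 0.3, with alpha 0.05 and power 0.8, and arrives at 88 participants or more. No strata enter this calculation.
- **Sample size** reports 98 enrolled: "48 subjects were randomized to the control condition and 50 subjects" to the experimental condition.
- **Primary outcome** is abstinence measured as "negative cocaine UAs tested twice weekly for 12 weeks". Under the experimental condition, a participant who discloses recent use need not give a sample; the "UA will be coded as positive by research staff".
- **Secondary outcome**: "Retention was defined as the number of weeks elapsed between treatment intake and dropout".
- **Statistical analyses plan** consists of two sentences. One begins "The primary endpoint of this study will be objectively verified abstinence based on the UA results collected twice weekly"; the other reads "Secondary endpoint will be duration of treatment retention". Neither gives a test, model, covariate, stratum or effect scale.

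Gender and baseline UA are therefore named as design factors once, in the randomization sentence, and are not mentioned in connection with any analysis.

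**The concern.** Stratified blocks force the arms to be nearly balanced on baseline UA and gender. If a balanced factor predicts the outcome, the arm difference varies less from trial to trial than an unadjusted standard error assumes. The estimate remains unbiased, but the interval is too wide, the test rejects less than 5% of the time under the null, and some power is lost.

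Baseline UA is an obvious candidate, because it is the same measurement as the outcome taken before treatment. The sponsor evidently thought it worth balancing. At stake is efficiency: a higher chance of missing a true effect smaller than the one the trial was sized for. Leaving the choice open also allows adjusted or unadjusted results to be selected after the data are seen.

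The absence of any declared primary model is a wider gap. This point concerns only what the analysis should inherit from the randomization, and on which effect scale.

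**Working it through.** **1. The plan's own figure.** Inputs from the Power section: alpha 0.05 (a 1-df chi-square is two-sided), power 0.80, w = 0.3.

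N = (1.960 + 0.842)² / 0.3² = 7.849 / 0.09 = 87.2, rounded up to 88. This matches. By the noncentral chi-square, power is 80.4% at N = 88 and 84.4% at N = 98.

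**2. Size of the loss by formula.** Let R² be the share of outcome variance explained by the strata. With stratified randomization:

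- unadjusted power = Φ((w√N − 1.96) / √(1 − R²))
- adjusted power = Φ(w√N / √(1 − R²) − 1.96)
- unadjusted type I error = 2Φ(−1.96 / √(1 − R²))
- unadjusted interval width relative to adjusted = 1 / √(1 − R²)

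At N = 98, w√N = 0.3 × 9.899 = 2.970. R² is not in the documents, so a range is shown:

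| R² | Power, unadjusted | Power, adjusted | Type I error, unadjusted | Unadjusted interval wider by |
|---|---|---|---|---|
| 0 | 84.4% | 84.4% | 5.0% | 0% |
| 0.05 | 85.0% | 86.1% | 4.4% | 2.6% |
| 0.10 | 85.6% | 87.9% | 3.9% | 5.4% |
| 0.20 | 87.1% | 91.3% | 2.8% | 11.8% |
| 0.30 | 88.6% | 94.4% | 1.9% | 19.5% |

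**3. Simulation, one binary result per person.** Assumptions, none from the documents: N = 98, blocks of 4 within baseline UA × gender, 20% women, 40% baseline-negative, 35% control abstinence overall, and a constant treatment odds ratio. Baseline-UA odds ratios of 2, 3 and 6 correspond to control abstinence of 45/29, 50/25 and 59/19% (baseline-negative/positive). Pearson chi-square against Cochran-Mantel-Haenszel (CMH), 20,000 runs:

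| Odds ratio | Type I error | Power, 35 vs 65% (w = 0.3) | Power, 20-point effect |
|---|---|---|---|
| 2 | 4.6 vs 4.9% | 86.8 vs 86.7% | 52.5 vs 52.7% |
| 3 | 4.3 vs 5.0% | 87.6 vs 88.1% | 52.9 vs 54.3% |
| 6 | 3.1 vs 4.8% | 87.9 vs 90.4% | 52.8 vs 58.3% |

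Step 2 agrees. For odds ratio 6, R² = 0.4 × 0.6 × (0.59 − 0.19)² / (0.35 × 0.65) = 0.0384 / 0.2275 = 0.169, and 2Φ(−1.96 / √0.831) = 3.2%, against 3.1% simulated.

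**4. Simulation, 24 UAs per person.** Same assumptions, plus within-person correlation 0.5. The analysis used independence estimating equations with a small-sample-corrected robust SE, 10,000 runs, on the risk-difference scale, unadjusted vs adjusted:

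| Odds ratio | Type I error | Power, 20-point effect | Adjusted interval narrower by |
|---|---|---|---|
| 2 | 4.4 vs 4.6% | 77.4 vs 78.4% | 1% |
| 3 | 3.8 vs 4.7% | 76.7 vs 79.9% | 5% |
| 6 | 2.2 vs 4.7% | 75.1 vs 84.3% | 14% |

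The gain exceeds that in step 3 because averaging 24 results removes visit-to-visit noise, so baseline UA explains more of what remains.

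**5. Sensitivity, odds ratios 2, 3, 6 (narrowing of the risk-difference interval).**

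- Correlation 0.3: 3, 8, 20%. Correlation 0.7: 1, 4, 11%.
- Baseline-negative share 20% or 60%: 1, 3–4, 10–11%. Share 10%: about 0–1, 1–2, 6–7%. Share 5%: about 0, 1, 3%.
- Half the participants leaving at a random visit, unrelated to arm or baseline UA: 1, 5, 14% with observed UAs only; 1, 3, 10% with missing counted as not negative.

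**6. Log-odds scale.** Adjustment raises power (76.4 vs 77.5, 75.6 vs 78.9, 73.8 vs 83.2% at 20 points) but need not narrow the interval. Adjusted-to-unadjusted width ratios are 1.02–1.06 at correlation 0.5, 0.97–1.01 at 0.3 and 1.03–1.11 at 0.7. Without the small-sample correction, the adjusted logit model's type I error is 5.6–5.9%.

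No magnitude was computed for retention.

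**The case against.** The strongest reply is that these factors are missing from the analysis only because no analysis is described; declaring a primary model would settle the covariates in the same sentence. That is partly right, but the wider gap could be closed with an unadjusted model and this loss would remain. Which factors to carry over, and on which scale, is a separate decision.

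Second, the harm is doubly conditional: it needs an unadjusted analysis and a prognostic baseline UA, and the documents establish neither. This stands, and the conclusion is worded accordingly.

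Third, w = 0.3 is the only effect size in the documents. With one binary result per person, the gain there is −0.1, +0.5 and +2.5 percentage points, and unadjusted power stays above 80%. This stands too. The larger losses need repeated UAs, a smaller effect and stronger prognosis, all of them assumed.

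Fourth, eligibility requires current moderate to severe disorder, so few participants may be UA-negative at baseline. A share of 5 or 10% shrinks the gain, as step 5 shows, without reversing it.

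Fifth, the dropout scenario takes dropout as unrelated to arm, although the intervention is meant to raise attendance. That limits those figures to the scenario simulated; the main result does not depend on them.

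Lastly, data collection is reported as finished, so the change may be possible only as a labelled post hoc analysis.

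**Conclusion.** The concern holds as an efficiency point. The plan stratifies on the baseline value of its primary outcome and specifies no analysis that uses it. An unadjusted analysis would be conservative, with no bias and no inflated type I error. Neither the sample size of 88 nor a positive result is called into question.

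Under the stated assumptions, the loss is almost nil at a baseline-UA odds ratio near 2, small to modest from about 3 to 6, and larger only with very strong prognosis. As an outer bound, at odds ratio 13 the adjusted risk-difference interval is about 25% narrower and power at 20 points is 73.9 vs 90.3%. Confidence is medium, because prognostic strength, within-person correlation and the baseline-negative share are all assumed. The precision claim applies to the risk difference; on the log-odds scale the gain is in power and a type I error close to 5%.

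**What to change.** State the primary analysis as a model of the repeated UA results, clustered by participant, with arm, baseline UA result and gender as terms. Report a risk difference, either from an identity link or as a standardized marginal difference from a logit model, with a small-sample-corrected robust SE. If a log odds ratio is reported instead, do not claim a narrower interval for it. If the endpoint is reduced to one defined binary result per participant, use a CMH test across the randomization strata. Include the same two factors in the retention analysis.

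Date the change, because the Study duration section reports that data collection ended in March 2020. If it is made after unblinding, label it post hoc and show the unadjusted result beside it.

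The cost is low: one model statement with a named effect scale. No new data are needed, since both variables had to be known for each participant in order to stratify.

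### Does the stated voucher maximum of about US$185, against US$174 from the printed schedule, call for a change to the plan?

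*Combined protocol and SAP*

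**What the plan says.** The Experimental condition section sets out the voucher rules. "The value of the vouchers will start at" is followed by about US$2.00 for the first negative UA. Vouchers then rise by about US$1.00 "for every consecutive negative cocaine UA submitted up to a maximum of" about US$5.00. A further amount of about US$5.00 is described as follows: "bonus will be given if both weekly UAs test negative for cocaine". A missed or positive UA resets the voucher to about US$2.00. The section closes with a summary: "If abstinent for the entire 12 weeks of treatment participants can earn up to" about US$185.00.

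The number of payments comes from elsewhere in the document. Treatment lasts 12 weeks (Intervention), and the Primary outcome section refers to "negative cocaine UAs tested twice weekly for 12 weeks". The Data collection section agrees: "Data were collected at baseline and twice weekly during the 12 weeks of the intervention".

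Each dollar amount carries an approximation sign. The section also explains that, as of December 2020, "one US dollar was approximately five Brazilian reais". No amounts in reais are given.

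**The concern.** The vouchers are the only thing that separates the two arms, so their size is in effect the dose of the intervention. If the schedule and its stated maximum disagree, a reader cannot tell from the text which one describes what participants were offered. Someone wishing to repeat or cost the programme gets two answers: for the 50 participants in the experimental arm, 50 × 185 = US$9,250 or 50 × 174 = US$8,700 at most. The stated total also exceeds what the schedule would give if every voucher were paid at its cap, so the gap looks like more than a miscount of the early steps.

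**Working it through.** **Inputs.** Start 2, step 1, cap 5, weekly bonus 5, all in approximate US dollars (Experimental condition). UAs: 2 per week × 12 weeks = 24. Possible weekly bonuses: 12 (Intervention, Primary outcome).

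**Attempt to reproduce the stated figure, taking the printed values as exact.**
- Vouchers: the sum over i = 1 to 24 of min(2 + (i − 1), 5) = 2 + 3 + 4 + 21 × 5 = 114.
- Bonuses: 12 × 5 = 60.
- Total: 114 + 60 = US$174, not 185. Gap: 185 − 174 = 11, and 11/174 = 6.3%.
- All 24 vouchers at the cap: 24 × 5 + 60 = US$180.

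The tokens of about US$0.50 are given only after recent use is disclosed, so they add nothing for someone abstinent throughout.

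**Other ways of counting.**
- 25 UAs and 12 bonuses: 119 + 60 = 179.
- 24 UAs and 13 bonuses: 114 + 65 = 179.
- 25 UAs and 13 bonuses: 119 + 65 = 184.
- 26 UAs and 12 bonuses: 124 + 60 = 184.
- 26 UAs and 13 bonuses: 124 + 65 = 189.
- A bonus of 6: 114 + 72 = 186.
- A cap of 6: 134 + 60 = 194.

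None gives 185, and each needs something that the document does not describe.

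**Allowing for the approximation signs.** Suppose that the printed whole dollars are rounded values of amounts that share one scale factor k. The total is then 174k, and 185 requires k = 185/174 = 1.063. The components become 2 × 1.063 = 2.13, 1 × 1.063 = 1.06 and 5 × 1.063 = 5.32 (cap and bonus alike). These round to 2, 1, 5 and 5, as printed. The cap and bonus are the tightest constraint: 5k rounds to 5 for k from 0.9 up to 1.1, which allows totals from 0.9 × 174 = 156.6 up to 1.1 × 174 = 191.4. The stated 185 lies inside that range. The US$180 figure is therefore a ceiling only if the printed dollars are exact.

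**An illustration in local currency.** Assume steps of 10, 15, 20 and 25 reais with a bonus of 25 reais. The document gives no such amounts. The total is 174 × 5 = 870 reais.
- At 5.0 reais per dollar: 870/5.0 = US$174.
- At 4.7: 870/4.7 = US$185.1, with steps of 2.13, 3.19, 4.26 and 5.32.
- At 4.5: US$193.3. At 5.5: US$158.2.

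The rates that round to US$185 run from 870/185.5 = 4.69 to 870/184.5 = 4.72. One rate near 4.7 can therefore produce both the printed steps and the printed total.

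**The case for a change.** The best argument for acting is that the rounding explanation is possible but not shown. The amounts are printed to two decimals, which does not suggest rounding to whole dollars. Only one exchange rate is mentioned, about five reais per dollar, and at exactly five the assumed schedule in reais gives 174. That rate is dated December 2020, after data collection had ended in March 2020, so the dollar figures are a later conversion of amounts that appear nowhere. The secondary objective concerns feasibility in a public programme, and the token procedure is justified partly by cost, so the size of the incentive is of interest to readers.

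Part of this stands. The face-value sum is 174, the document leaves the gap unexplained, and a conversion rate near 4.7 is an assumption. What does not stand is the step from there to an unreliable intervention. The start value, increment, cap, bonus, reset, frequency and duration are all stated, and together they determine each payment. The maximum triggers no payment. The cost that was incurred would come from the vouchers issued. The US$9,250 and US$8,700 figures assume that all 50 participants were abstinent for 12 weeks, and the document contains neither a voucher budget nor a cost endpoint.

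**Conclusion.** The mismatch is real at face value: US$174 from the schedule against a stated US$185, a gap of US$11 or about 6%. It does not show that the schedule and the maximum are incompatible, because approximate amounts converted at one common rate can give both. That reading rests on the printed dollars being rounded, which the document neither states nor excludes.

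No change to the plan follows, because nothing depends on the maximum. The sample size of 88 comes from an effect size of w = 0.3 with 80% power at the 0.05 level. The endpoints are UA-verified abstinence and weeks of retention. Neither these nor the described analysis uses the US$185 figure, and correcting it would alter no result or conclusion. The two statements must be reconciled wherever the intervention is next described, most simply by giving the amounts in reais and showing the sum. That is an editorial correction, and the document does not show which figure is the one to correct.
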